### **2.5.4 St. Marks (Vaizey) Incontinence Severity Score**

The St. Mark's (Vaizey) Incontinence Severity Score is a measure of severity of FI symptoms, which has been shown to correlate with improvement in frequency of FI episodes and subjects' perceptions of relief. This score reflects the severity of FI and ranges from 0 (complete continence) to 24 (complete incontinence).

### **2.5.5 Optional 3, 6 and 9 Month Surveys**

For the completion of online surveys at interim timepoints, a single survey generated using Survey Monkey containing the Eclipse Experience Assessment and the Vaizey score will be sent to subjects via a secure e-mail link or letter for completion approximately every 3 months after registering for the study. The electronic surveys are designed in such a way that there is no way to link a specific computer's IP address to the survey responses. For patients unable or unwilling to use the online survey, paper copies can be mailed to their addresses, with a pre-paid return envelope.

Subjects will have a 4 week window during which they can complete the surveys (every 3 months +/- 2 weeks) from their Eclipse Fitting date (or renewal date). If the surveys for the associated time period are not completed within this 4 week window, they will be counted as missed data points. Subjects will receive at least one, and no more than 5, reminders (by email and/or mail) to complete the surveys throughout the 4 week window.

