## 2.4 Schedule of Events

At the Enrollment/Fitting visit, and subsequent in-office visits (as outlined below, in **Table 2**), patients and clinicians will access online surveys to complete the required data collection (or if necessary, use hard copies). Additionally, subjects will be sent an email with a link to the optional 3, 6, and 9 month surveys or mailed printed surveys, depending on chosen survey delivery method, to be completed at each of 3, 6, and 9 month time points as per the schedule in **Table 2**.

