**Table 2. Schedule of Events**  
(shaded columns indicate in-office visits)

	Enrollment / Fitting	Subsequent Fittings (if necessary)	Eclipse Visit	3 Mo	6 Mo	9 Mo	12 Mo
Informed Consent & HIPAA Authorization	X						
Bowel Health History	X						
Fitting Metrics	X	X	X				X
St. Marks (Vaizey) Assessment	X		X	X	X	X	X
Eclipse Experience Assessment (including PGI-I)		X	X	X	X	X	X

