### **2.5.2 Fitting Metrics**

Clinicians will be asked at fitting visits, Eclipse visits, and annual renewals to provide information on the fitting process. For example, how many Inserts were used, and what sizes.

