### **3.1 Analysis Population**

The Analysis Data Set (ADS) will include all subjects who consent to participate in the PURSUIT registry and have at least an initial fitting, or, in the case of a patient already using Eclipse, be administered an annual renewal Eclipse.

---

 Vaizey, CJ, et al Gut 1999;44:77-80 doi:10.1136/gut.44.1.77

 Maeda Y. Does the St. Mark's incontinence score reflect patients' perceptions? A review of 390 patients. *Dis Colon Rectum*. 2008 Apr;51(4):436-42

For any analyses that require a comparison to baseline data, or data collected at the initial fitting visit, patients who enroll at their Eclipse renewal will be omitted from the ADS, as they will not have baseline or fitting metrics.

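### Do two different start dates for the 3, 6 and 9 month surveys cause answered surveys to be scored as missed?

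*Protocol*

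**What the plan says.** Section 2.5.5 handles the interim surveys in two paragraphs. The first describes sending. It concerns one survey that holds the Vaizey score together with the Eclipse Experience Assessment, and states that this "will be sent to subjects via a secure e-mail link or letter for completion approximately every 3 months after registering for the study". The second sets the counting window as "every 3 months +/- 2 weeks) from their Eclipse Fitting date (or renewal date". If surveys are not completed within it, "they will be counted as missed data points". Subjects are to receive "at least one, and no more than 5, reminders (by email and/or mail) to complete the surveys throughout the 4 week window".

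No section says which visit supplies the Eclipse Fitting date. Table 2 offers a new user three candidates: the Enrollment / Fitting visit, an optional column headed "Subsequent Fittings (if necessary", and the Eclipse Visit. The synopsis runs each patient's year from the date of Eclipse fitting and does not name a visit either.

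Section 3.2 assesses the outcomes at 12 months. It leaves assessments at 3, 6 and 9 months as something that may additionally be done.

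**The concern.** Sending and counting appear to run on different clocks, and the counting clock starts from an undefined date. If that date is the Eclipse Visit, the clocks differ by the length of the fitting process. Staff could then follow the sending rule correctly and still deliver a survey before its window opens. A woman who answered at once, and did not answer again after a reminder, would be recorded as missing although she had replied.

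At stake would be the interim Vaizey and PGI-I summaries among new users, and the loss would fall on women who took longest to fit. There is some support for this reading. Section 2.5.5 pairs the fitting date with a renewal date, section 3.1 ties renewal to receiving a device ("in the case of a patient already using Eclipse, be administered an annual renewal Eclipse"), and section 1.5.3 places year-long use of the Eclipse Insert after the Fitting Period.

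**Working it through.** **Inputs**
- Sending: about 3, 6 and 9 months after registration (2.5.5). Months are taken as T = 91, 182 and 273 days; the month length cancels out.
- Window: 14 days either side of each point, from the Eclipse Fitting date or renewal date (2.5.5).
- Trial Insert wear: 1-2 weeks, with one or more sizes tried (1.5.3).
- Assumption: inserts are worn one after another without gaps.

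**The plan's own figure.** 2 x 14 = 28 days, which is the stated four weeks.

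**Formula.** Let g be the days from registration to the Eclipse Fitting date. The survey goes out on day T and the window is [T + g - 14, T + g + 14]. It is sent early only if T < T + g - 14, that is g > 14, and then by g - 14 days.

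**Reading A: the date is the first fitting.** Consent is obtained at the Enrollment / Fitting visit (Table 2) and registration follows consent (2.3), so g is about 0. The 3-month window is days 77-105 and the survey goes out on day 91, in mid-window. Nothing is lost.

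**Reading B: the date is the Eclipse Visit (3-month survey, sent day 91).**

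| g (days) | Window (days from registration) | Days early |
|---|---|---|
| 7 | 84-112 | 0 |
| 14 | 91-119 | 0 |
| 21 | 98-126 | 7 |
| 28 | 105-133 | 14 |

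At g = 28 the 6-month survey goes out on day 182 (window 196-224) and the 9-month survey on day 273 (window 287-315), each again 14 days early. One insert gives g = 7-14, never early. Two give 14-28, so 0 to 14 days early. Three would give 21-42, so 7 to 28 days early. In every early case the whole 28-day window is still ahead when the survey goes out.

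**Women enrolled at renewal.** Their start date is the renewal date, normally close to registration, so g is about 0 on either reading.

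**Which reading the text supports**
- Section 2.4 treats enrollment and fitting as one occasion: "At the Enrollment/Fitting visit, and subsequent in-office visits".
- Section 2.5.2 keeps fittings apart from Eclipse visits: "Clinicians will be asked at fitting visits, Eclipse visits, and annual renewals to provide information on the fitting process". Table 2 does the same with separate columns. A fitting date is then most naturally the date of a fitting visit.
- Section 3.1, read as a full sentence, sets having an initial fitting against "in the case of a patient already using Eclipse, be administered an annual renewal Eclipse". The counterpart of renewal is therefore the initial fitting, which is the same pairing as in the 2.5.5 window rule.
- Section 3.2 takes baseline from the initial Fitting Visit and contrasts that with joining at renewal.
- Section 2.3 puts the annual visit about one year after enrollment begins, and the synopsis counts one year from the fitting. Together these place the fitting at about enrollment.

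The evidence favors reading A.

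**The case for a change.** The strongest case for acting is that this is more than silence. The protocol states a sending rule, a window and a rule for discarding late or early replies, and words the first two from different dates. Mailing staff and those scoring the windows could each follow the text and disagree. Any loss would be selective: under reading B with back-to-back wear, g > 14 needs more than one Trial Insert, and fitting is itself a registry outcome. It would also fall wholly on new users, the only women in analyses of change from baseline (3.1, 3.2). Naming one visit would cost almost nothing.

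The mismatch in wording stands, and so does the 14-day threshold. The consequence does not follow from them. A lost data point needs all of these together: the less supported reading; fitting longer than 14 days; sending held strictly to registration although the text says approximately; a reply before the window opens; and no second reply after at least one reminder inside it. The selectivity argument depends on the same chain. The values of g are also weakly founded, because the wear time comes from the device description, which mentions an episode diary that this registry's schedule does not contain.

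**Conclusion.** No change to the plan is called for. Two phrases in section 2.5.5 are not harmonized and one term lacks a definition, but the rest of the protocol supports an ordinary reading, the first fitting visit for new users and the renewal visit for the others. On that reading the clocks nearly coincide and the loss is zero. This is a gap that those running the registry can fill sensibly.

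On the other reading the survey would go out 0 to 14 days early with two Trial Inserts, or 7 to 28 days early with three, assuming back-to-back wear. The full window and at least one reminder would remain. The share of new users with g above 14 days is not given, so no count of affected surveys can be made. The surveys are optional and the interim assessments discretionary, while the 12-month assessment is essentially unaffected, so no gain from an amendment can be shown.

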## **3 Statistics**

---

### **3.1 Analysis Population**

The Analysis Data Set (ADS) will include all subjects who consent to participate in the PURSUIT registry and have at least an initial fitting, or, in the case of a patient already using Eclipse, be administered an annual renewal Eclipse.

---

 Vaizey, CJ, et al Gut 1999;44:77-80 doi:10.1136/gut.44.1.77

 Maeda Y. Does the St. Mark's incontinence score reflect patients' perceptions? A review of 390 patients. *Dis Colon Rectum*. 2008 Apr;51(4):436-42

For any analyses that require a comparison to baseline data, or data collected at the initial fitting visit, patients who enroll at their Eclipse renewal will be omitted from the ADS, as they will not have baseline or fitting metrics.

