### PURSUIT Protocol Synopsis

Study Objective	A Registry to Further Develop the Understanding of the Real World use of the Eclipse™ System for Fecal Incontinence in Women
Study Design	A prospective, open label post-market registry to collect Patient Reported Outcomes and Fitting metrics (e.g. sizes used) in subjects using the Eclipse System in a commercial setting
Sites/ Subjects	Up to 150 subjects enrolled, in up to 25 sites
Study Population	All adult female patients with Fecal Incontinence who present at, or are identified at, participating sites are eligible. This includes patients who are newly prescribed Eclipse, and those already using Eclipse who return for an annual renewal visit during the enrollment period.
Study Duration	Per-patient registry participation will last one year from the date of Eclipse fitting. Sites will be allowed to enroll patients until the earlier of: 12/31/2019 or enrollment of 150 patients.
Outcomes Measures	

1. Fitting Metrics

2. Change from baseline in mean scores on subject-reported outcomes related to symptoms as reported by St. Mark's (Vaizey) Incontinence Severity Score

3. Eclipse Experience Feedback Assessment, including the Patient Global Impression of Improvement (PGI-I)

Eligibility Criteria	

1. Adult female

2. Diagnosis of Fecal Incontinence

3. Clinician recommendation of the Eclipse System

4. Subject provides informed consent and HIPAA authorization

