### **1.5.3 The Trial Insert**

Prior to providing the Eclipse Insert to a subject, the clinician will use the Sizers and the Trial Insert to assess appropriate fit of the Eclipse Insert for each subject. The Trial Insert is composed of a base made of medical grade silicone, polycarbonate, and stainless steel, and a balloon made from medical grade silicone and polyurethane.

[figure not shown]
The Trial Insert consists of base-balloon configurations sized exactly as the Eclipse Inserts are sized and is intended for short-term use (1-2 weeks). This disposable Trial Insert allows the subject to try one or more Insert sizes (while keeping a fecal incontinence episode diary) during the Fitting Period before qualifying for and committing to the year-long use of the Eclipse Insert.

A silicone inflation tube connects to the balloon on one end, and to a self-closing luer valve (Valve) and cap on the other end which extends outside of the subject’s vagina. An optional extension tube can be added between the existing tube and the Valve to increase the length. The Valve allows the user to inflate or deflate the balloon with the Pump.

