### **2.2 Target Population**

Up to 150 subjects may be enrolled. All women being approached for inclusion into the PURSUIT registry must be adult female patients at participating sites and must have a diagnosis of Fecal Incontinence. She must be a new user of Eclipse or a patient returning to the clinic for her annual f/u visit. All participants will be required to provide informed consent and HIPAA authorization.

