### **2.3 Recruitment and Enrollment**

All patients who are deemed new suitable clinical candidates for the Eclipse System at a participating site will be invited to participate, as well as patients who are already using Eclipse, and return for an annual renewal visit during the enrollment period.

Potential subjects will be presented with information about how to sign up for the registry. . Each subject will be directed to a study-specific URL (searchable web page) where they can read an electronic Informed Consent Form and HIPAA Authorization Form. If they click on the "I agree to participate", "I consent", or similarly worded button they are taken to a registration form and are asked to provide their full name, date of birth, address, phone number and email address.

By navigating to and completing the registration page, this signifies the subject's willingness to participate in the online surveys and to receive future emails with the links to the online surveys to be completed, as well as to be contacted by the Sponsor by phone, email or in writing to remind

them to complete the surveys, and/or to provide clarifications about the information they have been provided in the completed surveys.

If a subject does not have access to, or is unwilling to provide, an email address, they can review a paper version of the Informed Consent Form and HIPAA Authorization form, and will be given an option to receive paper versions of all study surveys which can be filled out by hand and mailed back to the Sponsor. Similarly, if a site cannot easily access the URL, they can use the paper versions of all forms / surveys as well.

Enrollment in the post market registry, including the online data capture, will last for up to one year, and recruitment will end on 12/31/2019 or after 150 patients have been enrolled.

Sites will receive compensation for completing site surveys at each patient visit. Subjects will receive compensation for their time to complete each online (or returned hard copy) survey, which will be outlined in the Informed Consent form.

Enrollment will be completed once the annual visit is complete (approximately 1 year after enrollment begins).

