### **3.2 Outcomes Measurements**

Outcomes Measurements will be assessed at 12 months. Additional assessments may be made for interim (3, 6, 9-month) time points. Where applicable, changes from baseline will be evaluated. Baseline data will be defined as data provided at the initial Fitting Visit. If the patient was previously using the Eclipse System (e.g. joins the registry at a yearly follow-up/renewal), her baseline values will be omitted, and she will be excluded from analyses that require a baseline value.

The PGI-I, assessed as part of the Eclipse Experience Assessment, assesses changes from baseline in the control of bowel leakage, but does not have a baseline measurement. Instead, it is rated on a 7-point scale, where 1 is "Very much better" and 7 is "Very much worse". For a given time point, the average PGI-I score will be computed as the mean score across all completed assessments. Other Eclipse Experience Assessment questions will be summarized descriptively.

Fitting Metrics will be collected at the fitting visits, and summarized using descriptive statistics.

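### Does the Analysis Data Set wrongly leave out existing Eclipse users who enrol at an annual visit but are not renewed?

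*Protocol*

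**What the plan says.** Protocol section 3.1 builds the ADS from consenting subjects by two routes. A new user needs at least an initial fitting. An existing user must, "in the case of a patient already using Eclipse, be administered an annual renewal Eclipse". The same section removes women who enrol at renewal from any analysis that needs baseline or initial-fitting data, and section 3.2 repeats that exclusion.

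Enrolment is worded around the visit:

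- Section 2.2: "She must be a new user of Eclipse or a patient returning to the clinic for her annual f/u visit".
- Section 2.3 invites "patients who are already using Eclipse, and return for an annual renewal visit during the enrollment period".
- Section 3.2 describes the existing user as one who "joins the registry at a yearly follow-up/renewal".
- The Synopsis lists "Clinician recommendation of the Eclipse System" among the eligibility criteria for everyone.

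On the new-user side, section 1.5.3 says the Trial Insert is worn "during the Fitting Period before qualifying for and committing to the year-long use of the Eclipse Insert". A fitting therefore does not imply that the year-long device followed.

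**The concern.** The two routes are not equally demanding. A new user who is fitted, tries the device and stops remains in the ADS. An existing user who attends her annual visit, consents and is not given a renewal drops out of it. Renewal can come after consent and may depend on how well the device worked, so the rule could select satisfied users after enrolment. A registry of real-world use would want to avoid that.

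At stake are the outcomes that existing users can contribute to: the PGI-I mean, the other Eclipse Experience items and the count of subjects. Two smaller points go with it. Section 2.5.5 times the survey windows from a fitting or renewal date, and a woman who was not renewed may have neither within the registry. Table 2 schedules the "St. Marks (Vaizey) Assessment" at enrolment, yet section 3.2 sets aside an existing user's value as a baseline.

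**Working it through.** The protocol has no figure of its own to reproduce, so the first check sets the provisions side by side.

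1. **Entry rules.** New user: consent plus a fitting. Existing user: consent plus a renewal. Each needs one device event inside the registry. A new user who consents but is never fitted is left out too. The routes differ in how much the event demands, but both rest on exposure.
2. **Who can fall in the gap.** The Synopsis and section 2.3 both speak of an annual renewal visit, section 3.2 treats follow-up and renewal as one occasion, and eligibility requires a clinician recommendation. The gap arises mainly from the looser follow-up wording in section 2.2.
3. **Which outcomes are touched.** Change in Vaizey score and initial-fitting summaries already exclude all existing users. In Table 2 the row beginning "Eclipse Experience Assessment (including PGI-I" has no entry at the enrolment visit, so only later responses could be lost.
4. **Which time point.** Section 3.2 assesses outcomes at 12 months and makes the 3-, 6- and 9-month assessments optional. Section 2.5.3 counts the 12-month visit as in-office. A woman without a renewed device may have little reason to attend.

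The second check is an illustration. Only the cap of 150 subjects comes from the protocol. The other inputs are assumptions:

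- p, share of existing users: 20% to 50%
- q, share of those not renewed: 5% to 20%
- d, how much worse non-renewed women score on PGI-I than all others: 1 to 3 points
- r, their survey completion relative to the others: 0 to 1

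Women left out = 150 × p × q:

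- 150 × 0.2 × 0.05 = 1.5
- 150 × 0.2 × 0.10 = 3
- 150 × 0.5 × 0.10 = 7.5
- 150 × 0.5 × 0.20 = 15

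Shift in the pooled PGI-I mean = d·p·q·r / (1 − p·q + p·q·r):

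| d | p | q | r | Calculation | Shift |
|---|---|---|---|---|---|
| any | any | any | 0 | numerator is 0 | 0 |
| 1 | 0.2 | 0.05 | 0.5 | 0.005 / 0.995 | 0.005 |
| 2 | 0.2 | 0.10 | 0.5 | 0.02 / 0.99 | 0.020 |
| 2 | 0.2 | 0.10 | 1.0 | 0.04 / 1 | 0.040 |
| 2 | 0.5 | 0.10 | 0.5 | 0.05 / 0.975 | 0.051 |
| 2 | 0.5 | 0.10 | 1.0 | 0.10 / 1 | 0.100 |
| 3 | 0.5 | 0.20 | 1.0 | 0.30 / 1 | 0.300 |

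The 0.300 needs half the registry to be existing users, one in five of them not renewed, a 3-point gap and full survey completion, all together. The last of these fits poorly with step 4.

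**The case for a change.** The strongest case for a change is that section 3.1 fixes this rule in the protocol, so it is not a detail left to a statistical analysis plan. The text does permit an enrolled woman to be outside the ADS, and no other section brings her back. Reading her past fitting as satisfying the new-user route is strained, because the sentence assigns existing users to the renewal route. A clinician recommendation is not the same as a device being supplied. A few sentences would align the sections and show how many women were not renewed.

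The textual mismatch stands. The argument that it biases results does not go far. The protocol does not say why a renewal might fail to happen, so a link with benefit is conjecture. Admitting these women would also have a cost: women without a renewed device would answer questions on comfort, satisfaction and use, which changes what those summaries describe. A larger selection would remain, because existing users can enrol only if they come back after a year.

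The accompanying points are matters of detail. The renewal date in section 2.5.5 can be read as the date of the renewal visit. A count of consented women who were not renewed is ordinary disposition reporting. Section 3.2 does not bar a descriptive summary of existing users' Vaizey scores, and a table of maintained control would be an added analysis. The remark in section 3.1 that renewal enrollees lack fitting metrics is loosely put, since section 2.5.2 collects these at renewals too. The same sentence refers to the initial fitting visit, so its meaning is clear.

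**Conclusion.** No change to the plan is needed. Sections 2.2 and 3.1 are worded differently, and a consented existing user who is not renewed can fall between them. Requiring a renewal is still a defensible way to define exposed users, and the alternative is a trade-off with no shown benefit.

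Any effect is confined to PGI-I, Eclipse Experience summaries and subject counts. Under the assumed ranges about 2 to 15 of 150 women are affected, and the PGI-I mean moves by 0 to 0.30 points. With 10% not renewed, a 2-point gap and half to full relative completion, the shift is 0.02 to 0.10. These figures show scale only, because all four inputs are assumed. The conclusion rests on non-renewed enrollees being few, as the renewal-visit wording and the clinician-recommendation criterion suggest, and on 12 months being the main time point.
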